6. COLLECTION OF STUDY VARIABLES

6.1 Recording of data

The electronic data capture (eDC) system will be used for data collection and query handling. The investigator will ensure that data are recorded on the eCRFs as specified in the CSP and in accordance with the instructions provided.

The investigator will ensure the accuracy, completeness, and timeliness of the data recorded and of the provision of answers to data queries according to the Clinical Study Agreement (CSA) or locally defined contract. The investigator will sign the completed eCRFs. A copy of the completed eCRFs will be archived at the study site.

6.2 Data collection at enrolment and follow-up

6.2.1 Enrolment procedures

Confirmation of clinical inclusion criteria

Any patient considered for enrollment into the study must provide written informed consent (signed and dated) prior to conducting any study-specific procedure.

6.2.1.1 Screening visit (Visit 1)

This section describes the preferred order of assessments; however, this order is not mandatory, except that QIDS-SR-16 and S-STS must be done first. Note, that the assessments to be performed during the screening visit can be completed over 2 days if agreed upon with medical advisor.

During the screening visit, the QIDS-SR-16 and S-STS (self report) will be administered first.

Prior to conducting any further procedures, the QIDS-SR-16 should be independently scored (without review by the investigator) and if the inclusion criterion score of ≥ 19 is not met, no further study procedures are to be conducted and the patient will not be randomized. At no time may the patient be informed of the inclusion criterion score on the QIDS-SR-16. If the QIDS-SR-16 criterion is met, the HAM-D-17 interview will be conducted and the CGI-S will be completed to determine whether the patient meets the inclusion criteria of a HAM-D-17 total score ≥ 24 and CGI-S ≥ 5 . If these criteria are not met, no further procedures are to be conducted and the patient will not be randomized. If these criteria are met, the MINI interview will be conducted.

While completing Module B of the MINI (suicidality), the investigator will review the S-STS self report responses and inquire further into any suicidal ideation that was reported. During this portion of the interview, the investigator will also complete the C-SSRS baseline version. If the patient is judged by the investigator to pose a significant suicide risk, the patient will not be enrolled and the investigator will take appropriate steps to assure the patient's safety. Evidence of significant suicide risk may include any history of suicidal attempt or behavior and/or any suicidal ideation of type 4 or 5 on the C-SSRS in the last 6 months.

██████████

If the patient is judged not to pose a significant suicide risk, the MINI interview is completed to confirm that the patient meets diagnostic inclusion criteria for the study (DSM-IV-TR 296.2 or 296.3), and to confirm the absence of lifetime history of previous manic or hypomanic episodes (Module C), the absence of current alcohol abuse or dependence (Module I), the absence of current substance dependence/abuse (Module J) and the absence of current mood disorder with psychotic features (Module K). Note that history of alcohol or substance abuse or dependence for the past 6 months is also exclusionary and that determination should be made at this point.

If the patient still meets inclusion criteria for the study, the ATHF should be completed with the patient. If based upon the patient's self report and the investigator's best judgment the patient is deemed reasonably likely to meet the inclusion criterion of at least 2 previous (in addition to the current) antidepressant treatment regimens of adequate dose and duration (as specified in Table 1 and Table 3), all remaining clinical and laboratory assessments listed in Table 4 should be completed and arrangements should be made with the patient to obtain the necessary documentation from previous inadequate responses (e.g. contact information of previous treating physicians and signed releases that may be necessary to obtain written medical records). Acceptable evidence of previous inadequate responses may include verbal or written communication with the treating physician (recorded in the source document), or copies of medical or pharmacy records.

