6.2.2.2 Sheehan Suicide Tracking Scale (S-STs) Self report form

The S-STs is a prospective, patient self-report or clinician-administered rating scale that tracks suicidal ideation and behaviors and has been shown to be sensitive to clinical change with treatment ([Coric et al 2009](#), [Khan et al 2011](#)).

Only the self-report portion of the scale will be used in this study, which must be reviewed and signed by the investigator prior to conducting the C-SSRS interview. The S-STs will be administered at designated visits prior to the infusion. Note that the C-SSRS should be administered after the infusion.

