6.2.2.3 Hamilton Rating Scale for Depression (HAM-D-17)

The HAM-D-17 is a 17-item observer-rated scale that assesses depressive symptoms ([Hamilton 1960](#)) each of which is rated from 0 to 2 to 0 to 4, where 0 is none/absent. Depressive symptoms include depressed mood, feelings of guilt, suicide, insomnia-early, insomnia-middle, insomnia-late, work and activities, retardation, agitation, anxiety psychic, anxiety somatic, somatic symptoms-gastrointestinal, somatic symptoms-general, genital symptoms, hypochondriasis, loss of weight, loss of insight, diurnal variation,

depersonalization and derealization, paranoid symptoms, and obsessional symptoms. The first 17 items contribute to the total score. The HAM-D-17 will be performed during the screening (Visit 1) and randomization visits (Visit 2) to determine whether the patient meets the severity inclusion criterion of a total score of ≥ 24 .

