Worsening symptoms of the primary study condition (ie, MDD) should not be recorded as an AE. However, if hospitalization results from worsening psychiatric symptoms, the hospitalization should be recorded as an SAE in the eCRF.

Study drug abuse is an SAE, even when there are no symptoms or additional AEs, and should be reported according to the guidelines in Section 6.4.4. Misuse of IP is an AE, but is not considered an SAE unless accompanied by serious sequelae.

Should an overdose of IP occur, it must be reported in accordance with the procedures described in Section 13.2. An overdose associated with symptoms must be reported as an AE, while an overdose without associated symptoms, must be reported only on the separate AstraZeneca Clinical Study Overdose Report Form.

Suicidality

Any patient who, based on the investigator's judgment, poses an imminent risk of suicide should be discontinued from the study (see Section 5.8 and Section 5.9). All efforts should be taken to minimize the risk of suicide and the investigator should carefully monitor the

patient. If during the course of the study, a patient shows evidence of serious suicidality (for example warranted by a scoring of 4 or 5 on the C-SSRS), the patient should be referred to their attending psychiatrist, a local emergency room etc. for further evaluation to see if they are safe to continue in the study. The site should have the ability to direct any patient that requires emergency hospitalization to an emergency room or inpatient psychiatric unit that is within a 50 mile radius of the site. In addition, the patient should be able to contact someone at the site 24 hours per day should they have serious worsening of their condition.

Suicide and attempted suicide, irrespective of the method, but occurring in connection with the use of IP, should be reported as AEs (serious or nonserious). This event should be identified as suicide or attempted suicide, and the method of the suicide or attempt should be provided. If an attempted suicide meets the criteria for an SAE, the event must be reported according to the guidelines in Section 6.4.4. Strong suicidal thoughts should also be regarded as AEs.

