10. DATA MANAGEMENT BY ASTRAZENECA OR DELEGATE

Data management (DM) will be performed by the CRO. The data collected through third party sources will be obtained and reconciled against study data.

Data entered in the eDC system will be immediately saved to a central database and changes tracked to provide an audit trail. When the PI has signed the eCRF electronically as per eCRF instructions, then the patient's data will be locked.

Electronic case report form (eCRF)

The eCRF and the protocol are both confidential. The eCRF will be created by the CRO and programmed into the eDC system. All sites will need internet access to access the eCRFs and will only have access to data for patients at their own sites. Data management and other co-ordinator teams will have access to data at all sites.

AstraZeneca or its representative will supply the eCRFs. All eCRFs are to be completed by an authorized member of the site staff and reviewed and signed by the investigator. All entries,

corrections, and alterations are to be made by the responsible investigator or an authorized member of the site staff. All eCRFs are to be completed in a manner that ensures accurate interpretation of data.

It is each investigator's responsibility to ensure that all discontinued orders or changes in the study or other medications entered on the patient's eCRF correspond to the entries on the patient's medical records.

The eCRFs for any patient leaving the study should be completed at the time medication is terminated for whatever reason.

The eCRFs must accurately reflect data contained in the patient's records (eg, source documents).

Dataflow

The data will be validated as defined in the DM Plan. Quality control procedures will be applied to each stage of data handling to ensure that all data are reliable and have been processed correctly.

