11.1.2 QIDS-SR-16

The QIDS-SR-16 total score is derived from the 16 individual items as instructed on the instrument scoring sheet. The change from baseline to each assessment will be calculated as the visit score minus the baseline score.

The QIDS-SR-16 total scores range from 0 to 27. The total score is obtained by adding the scores for each of the 9 symptom domains of the DSM-IV-TR MDD criteria: depressed mood, loss of interest or pleasure, concentration/decision making, self-outlook, suicidal ideation, energy/fatigability, sleep, weight/appetite change, and psychomotor changes (Rush et al. 2003). Sixteen items are used to rate the 9 criterion domains of major depression: 4 items are used to rate sleep disturbance (early, middle, and late insomnia plus hypersomnia); 2 items are used to rate psychomotor disturbance (agitation and retardation); 4 items are used to rate appetite/weight disturbance (appetite increase or decrease and weight increase or decrease). Only 1 item is used to rate the remaining 6 domains (depressed mood, decreased interest, decreased energy, worthlessness/guilt, concentration/decision making, and suicidal ideation). Each item is rated 0 to 3. For symptom domains that require more than 1 item, the highest score of the item relevant for each domain is taken. For example, if early insomnia is 0, middle insomnia is 1, late insomnia is 3, and hypersomnia is 0, the sleep disturbance domain is rated 3. The total score ranges from 0 to 27.

The total score is calculated as follows from the following 9 scores.

The maximum score of the 4 sleep items (item 1 to item 4)

The score for item 5

The maximum score of the 4 appetite/weight items (item 6 to item 9)

The scores for item 10 to item 14

The maximum score of the 2 psychomotor items (item 15 and item 16)

Total scores range from 0 to 27.

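### A patient stopped at the Visit 1 QIDS-SR-16 gate can leave after completing a suicidality self-report that no step requires a clinician to read before departure

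*Protocol*

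**What the plan says.** Section 6.2.1.1 sets out Visit 1 as a preferred order with one fixed element: "this order is not mandatory, except that QIDS-SR-16 and S-STS must be done first". The QIDS-SR-16 is then scored independently, without the investigator seeing it, before anything else happens. If the total is below 19, "no further study procedures are to be conducted and the patient will not be randomized". If it is 19 or more, the HAM-D-17 interview and CGI-S follow, with a similar stop for a HAM-D-17 total below 24 or a CGI-S below 5. Only patients who pass both gates reach the MINI.

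The S-STS is taken up inside the MINI: "While completing Module B of the MINI (suicidality), the investigator will review the S-STS self report responses". In the same part of the interview the investigator asks about any reported ideation, completes the baseline C-SSRS, and protects the patient if the risk is judged significant.

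The general rule on the S-STS is in Section 6.2.2.2. The protocol uses the self-report form, "which must be reviewed and signed by the investigator prior to conducting the C-SSRS interview".

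**The concern.** The protocol asks severely depressed people to put suicidal thoughts on paper, then for some of them ends the visit before the step at which the paper is read. The first gate is applied to a score the investigator is deliberately kept from reviewing, so a patient stopped there need not have had any clinical interview at that visit.

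What is at stake is the safety of screen failures. If the stop rule is followed literally, a patient can disclose active suicidal ideation and go home with nobody obliged to have seen the disclosure. Section 5.9 expects no further follow-up of patients who leave the study before randomization, so there is no planned later contact at which the report would come to light.

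**Working it through.** There is no design figure to reproduce. The check traces the path of a stopped patient, looks for any other provision that would reach that patient, and asks whether a QIDS-SR-16 total below 19 rules out serious ideation.

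**Path of a patient with a QIDS-SR-16 total of 18 or less (6.2.1.1)**

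1. QIDS-SR-16 and S-STS completed: done.
2. QIDS-SR-16 scored without the investigator: done.
3. Total below 19: study procedures stop.
4. HAM-D-17 and CGI-S: not reached.
5. MINI Module B, with S-STS review and inquiry into ideation: not reached.
6. Baseline C-SSRS and the safety action that follows: not reached.

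A patient stopped at step 4 also misses steps 5 and 6, but has had a clinician interview that covers suicide. Section 6.2.2.3 lists the content: "Depressive symptoms include depressed mood, feelings of guilt, suicide, insomnia-early", and so on. The gap there is narrower.

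**Other provisions that might reach the stopped patient**

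- Section 6.2.2.2 makes review and signature compulsory but times them to the C-SSRS interview, which this patient does not have.
- Section 6.3.1 makes the same link to the C-SSRS, in a sequence that applies to visits after screening.
- Table 4 and Section 6.4.9.6 schedule a C-SSRS at screening, but the stop rule comes first. Section 3.1.1 reserves the full set of assessments for patients who meet preliminary eligibility.
- Section 6.4.3 calls for referral when a patient "shows evidence of serious suicidality (for example warranted by a scoring of 4 or 5 on the C-SSRS". That presupposes that someone has seen the evidence, and here no C-SSRS is done.
- Section 10 has eCRFs "completed by an authorized member of the site staff and reviewed and signed by the investigator". This carries no timing relative to the patient's departure and no link to suicide risk.

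None of these directs anyone to the S-STS before the patient goes.

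**Does a total below 19 exclude serious ideation?**

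Section 11.1.2 builds the total from nine symptom domains. On scoring it says: "Each item is rated 0 to 3". A domain with several items takes the highest of them.

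- Range of the total: 9 × 0 = 0 to 9 × 3 = 27.
- Suicidal ideation, a single-item domain, at its maximum: 3.
- Maximum of the other eight domains: 8 × 3 = 24.
- The patient is stopped if the total is at most 18, that is, if the other eight domains sum to at most 18 − 3 = 15.
- Boundary case: 3 + 15 = 18, which is below 19.

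With ideation at its maximum, every sum from 0 to 15 on the other domains gives a total of 3 to 18 and stops the patient. The threshold selects on overall severity, not on suicide risk.

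**The case against.** The strongest reply is that the protocol is not silent about the form or about suicidality.

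- Section 6.3.2 has scale scores entered in the eCRF and Section 10 has the investigator review and sign it, so someone reads the S-STS eventually.
- Section 6.3.3 names a coordinator responsible for patient-reported outcomes.
- Section 6.4.3 starts adverse event collection at consent, asks for suicidality to be monitored carefully, and requires 24-hour site contact.
- The stop rule ends study procedures, not care. Apart from the two forms that come first, the order is only preferred. Reading a completed form is nowhere forbidden, and 6.2.2.2 can be read as making the C-SSRS merely the latest moment for a review that is due anyway.
- The worked example is not the sharpest one: a patient scoring 3 on the QIDS-SR-16 ideation item has had that answer handled by whoever scored the form.

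Much of this stands as far as it goes. It would be wrong to say that nobody ever has to look at the S-STS, so the point has to be confined to review before the patient leaves. The scoring remark is also fair, although the protocol neither says who scores nor tells the scorer to pass on a positive item. The clearest case is a positive S-STS beside an unremarkable QIDS-SR-16 ideation item, where scoring would reveal nothing.

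What does not stand is that these provisions fill the gap. Permission to read the form is not a duty to read it. Data sign-off is not timed to the visit, the coordinator's role concerns bias and compliance, and the general duties depend on someone already knowing. At about 60 sites, reliance on individual good practice is a weak substitute for an instruction.

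**Conclusion.** The point holds. At Visit 1 a patient stopped at the QIDS-SR-16 gate can leave with a completed S-STS that no step requires a clinician to read first. The same is true, less seriously, at the HAM-D-17/CGI-S gate.

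The conclusion rests on the wording and sequence of 6.2.1.1, on reading 6.2.2.2 as tied to the C-SSRS interview, and on the scoring rule in 11.1.2. It makes no claim about how often this would happen. The protocol gives neither the number screened nor the number failing at either gate, so no count can be offered. The trial's estimates, error rates and power are untouched.

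It should be fixed: the number affected is unknown, the possible harm to an individual is grave, and the remedy is very small.

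**What to change.** Add two sentences to 6.2.1.1:

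1. The stop rules at Visit 1 end eligibility procedures only.
2. Before any Visit 1 screen failure leaves the clinic, the investigator reads and signs the completed S-STS, checks the suicidal-ideation item of the QIDS-SR-16 once it has been scored, and responds to a positive report as the Module B paragraph already provides.

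Reading the S-STS itself covers the patient whose QIDS-SR-16 ideation item is unremarkable. Checking that item only after scoring keeps the QIDS-SR-16 scoring independent of the investigator. The cost is the added text and a few minutes of investigator time per Visit 1 screen failure. No new instrument is needed and no analysis changes.

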6.2.1.2 Randomization visit (Visit 2)

Prior to the randomization visit, adequate documentation must be in place to confirm that the patient meets modified ATHF inclusion criteria of inadequate response to at least 2 previous antidepressant treatments of adequate dose and duration. In addition, results from all laboratory assessments conducted at the screening visit should be available and confirm that the patient continues to meet clinical and safety criteria for inclusion.

At the randomization visit, the QIDS-SR-16 will be administered first. Prior to conducting any further procedures, the QIDS-SR-16 should be scored (without review by the investigator) and if the inclusion criterion score of ≥ 19 is not met, no further study procedures are to be conducted and the patient will not be randomized. At no time may the patient be informed of the inclusion criterion score on the QIDS-SR-16. If the QIDS-SR-16 criterion is met, the HAM-D-17 interview will be conducted and the CGI-S will be completed to determine whether the patient meets the inclusion criteria of a HAM-D-17 total score ≥ 24 and CGI-S ≥ 5 . If these criteria are not met, no further procedures are to be conducted and the patient will not be randomized. If these criteria are met, the patient is randomized and the remaining clinical and laboratory assessments are conducted in accordance with Table 4.

The MADRS, CGI-S, S-STS, HAM-A, SDS, and Cogstate are conducted prior to the first infusion. After the first (and last) infusion, the patient must remain in the clinic for at least 3 hours after the infusion (T_4) during which time AEs are collected, and CADSS and C-SSRS are administered. Vital signs and orthostatic BP are measured at every infusion at multiple time points: T_0 , T_1 (vital signs only), and either at least 1 hour (T_2) after the end of infusion (all indicated visits, except for Visits 2 and 16), or, at least 3 hours (T_4) after the end of infusion (applies to Visits 2 and 16, which corresponds to first and last infusions).

6.2.2 Follow-up procedures

Description of clinical rating instruments used for diagnosis and entry criteria

The following instruments are administered during the screening and randomization visits (Visits 1 and 2, respectively) to evaluate the presence and severity of MDD and to establish inclusion and exclusion criteria. Several of these measures are also administered at follow-up visits to monitor study outcome, severity of clinical symptoms and safety. The timing of all instruments is specified in [Table 4](#).

All clinician ratings must be conducted by raters who are trained and certified to conduct the required clinical interviews and to make the required ratings. During the clinical interviews, the trained rater will record clinical observation on each scale, which will be used as the source documents. If at all possible, the same individual should perform each assessment at each visit to reduce scoring variability. In the event the primary rater is not available, a designated back-up rater who meets the same qualifications may perform the ratings.

6.2.2.1 Quick Inventory of Depressive Symptomatology-Self Report (QIDS-SR-16)

The QIDS-SR-16 is a 16-question self-report inventory (patient-reported outcome [PRO]) that includes the 9 DSM-IV-TR criteria symptom domains: sad mood, concentration, self-outlook, suicidal ideation, involvement, energy/fatigability, sleep disturbance (4 items: initial, middle, late insomnia, and hypersomnia), appetite/weight increased or decrease (4 items), and psychomotor agitation/retardation (2 items) ([Rush et al 2003](#), [Trivedi et al 2006](#)). At designated visits, the QIDS-SR-16 should be completed as soon as possible after the patient arrives at the clinic, prior to the infusion and before there has been significant clinical contact. It should be completed by the patient alone in a quiet, private space without influence from clinic staff or any person accompanying the patient, including family.

6.2.2.2 Sheehan Suicide Tracking Scale (S-STs) Self report form

The S-STs is a prospective, patient self-report or clinician-administered rating scale that tracks suicidal ideation and behaviors and has been shown to be sensitive to clinical change with treatment ([Coric et al 2009](#), [Khan et al 2011](#)).

Only the self-report portion of the scale will be used in this study, which must be reviewed and signed by the investigator prior to conducting the C-SSRS interview. The S-STs will be administered at designated visits prior to the infusion. Note that the C-SSRS should be administered after the infusion.

